- The first futility early stopping rule will be applied after treating 14 patients with the tri-therapy at the RP2D level. If none of the 14 patients has 6-month response (CR or PR), the patient enrollment will be halted and the trial can be stopped for futility.
- The second futility early stopping rule will be evaluated every 10 patients after 20 patients are treated at the RP2D by applying the predictive probability. The trial will be stopped early if we see the following 6-month responses or less: 2 in 20, 3 in 30, 5 in 40, 6 in 50, 7 in 60, 9 in 70, 11 in 80, or 12 in 90 patients.

If the trial is not stopped early after the first 100 patients, the study could be extended to an additional 100 patients treated with an amendment. Two possible scenarios can then be envisioned:

- Repeat identically all investigations for additional 100 patients, (exactly as for the first cohort), with the purpose to have a final cohort of 200 patients, which would give good statistical power for the study. With 5% one- sided type I error, we need to treat 20 patients to demonstrate the usefulness of the tri-therapy approach to achieve and 86% power based on the exact binomial test. With an expected 10% of patients who will be fully matched, we need to enroll 200 patients in the study.
- For the second cohort, use SIMS to stratifying patients and select only the subgroups with the highest efficacy as demonstrated after the study of the first cohort. This statistical model will be much more powerful to demonstrate usefulness of the tri-therapy approach. This scenario is also the most appropriate from an ethical perspective.

It is planned that after collecting data on about 50 patients, a meeting with the FDA will be organized in order to assess which scenario of design is recommended and to ask for a risk determination for need for IDE.

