#### Criteria of success:

- We will document best response in all patients. Patients shall be followed for at least six months on treatment (providing their tumors do not progress earlier) in order to document best response: The trial will be considered as meeting its primary endpoint if a 6-month response rate (% of patients achieving RECIST 1.1 complete or partial response within 6 months of treatment start) of 50% is achieved for patients who are fully matched according to the SIMS retrospective analysis and is superior to the partially matched arms. With a type I error of 10% and a power of 94%, 20 patients fully matched will be enough to demonstrate the usefulness of the approach assuming a null response rate of 20% based on the one-sided Fisher's exact test. This would require a cohort of 200 patients treated. Nevertheless, we intend to treat an initial cohort of 100 patients as an exploratory observational study. Pending clinical activity, the study could be extended to an additional 100 patients treated in order to attain sufficient statistical power to support the validity of the approach.
- SIMS will show clinical utility:
  - If the proportion of patients fully matched to the combination versus partially matched estimated using SIMS (20/80) is similar to the observed proportion in the SPRING cohort (maximum coefficient variability allowed 20%),
  - If fully matched patients show significantly better clinical outcomes than the partially matched ones and the fully or partially matched ones show significantly better clinical outcomes than the non-matched ones.

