### 7.2.1. Statistical analysis of the primary efficacy end point

The primary efficacy evaluation for measuring a clinical meaningful improvement is defined as demonstrating an improvement of the primary efficacy endpoint of 6-month objective response rate from 20% (under the null hypothesis) to 50% (under the alternative hypothesis) in the fully matched arm. With 5% one-sided type I error, we need to treat 20 patients to demonstrate the usefulness of the tri-therapy approach to achieve and 86% power based on the exact binomial test. With an expected 10% of patients who will be fully matched, we need to enroll 200 patients in the study. All inevaluable patients will be replaced. **To ensure that patients will not receive ineffective treatments after sufficient evidence, two efficacy futility early stopping rules** will be implemented.

- The first futility early stopping rule will be applied after treating 14 patients with the tri-therapy at the RP2D level. If none of the 14 patients has 6-month response (CR or PR), the patient enrollment will be halted and the trial can be stopped for futility. This futility early stopping rule coincides with the first stage of the Gehan's design targeting 20% response rate with 95% confidence (26).
- The second futility early stopping rule will be evaluated every 10 patients after 20 patients are treated at the RP2D by applying the predictive probability (27). The trial can be stopped early if we see the following 6-month responses or less: 2 in 20, 3 in 30, 5 in 40, 6 in 50, 7 in 60, 9 in 70, 11 in 80, or 12 in 90 patients. The design has 5% type I error rate and 95% power with a null response rate of 10% and a target response rate of 30% at 6 months in the whole group. The probability of early stopping is 0.95, 0.31, and 0.04 if the response rate in the whole group is 10%, 20%, and 30%, respectively.

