- In addition to the futility analysis for early stopping of the trial if the triple therapy does not show minimum efficacy in the whole group, we will also look for efficacy signal in the subgroups. The triple therapy will be considered potentially effective if the posterior probability of response rate greater than 0.3 is larger than 60% in any of the predefined subgroups (Arm A, Arms B1-B3, Arms C1-C3, or any of the combined groups). Assuming a weak prior of Beta (0.1, 0.9), the treatment will be considered potentially efficacious if we see 4 responses in 10 patients, 7 responses in 20 patients, or 10 responses in 30 patients.
- In rare occasions that the early futility stopping criterion is met but the treatment shows potential efficacy in predefined subgroups, further discussions will be conducted among study PIs, sponsors, and regulatory agencies to determine whether study will be terminated or extended in specific subgroups.

These cohort size estimates are based on *in silico* data generated by SIMS using an independent set of data obtained from investigation of tumor and matched normal biopsies from the same patient. SIMS model will be considered clinically meaningful if the observed matches are similar to estimated matches, with a maximal tolerated coefficient of variability of 20%, and if fully matched group shows better outcome than partially matched groups.

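### Sections 3.1 and 7.2.1 give different type I errors, powers and test names for the same primary test in 20 fully matched patients, so 7 responders in 20 passes one rule and fails the other

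*Combined protocol and SAP*

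**What the plan says.** Section 3.1 (Criteria of success) defines when the trial meets its primary endpoint. It refers to a 6-month response rate "of 50% is achieved for patients who are fully matched according to the SIMS retrospective analysis and is superior to the partially matched arms". The design sentence follows: "With a type I error of 10% and a power of 94%, 20 patients fully matched will be enough to demonstrate the usefulness". Its null is worded as "assuming a null response rate of 20% based on the one-sided", and the test it names is Fisher's. It adds that this requires 200 treated patients.

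Section 7.2.1 describes the primary efficacy analysis as an improvement in 6-month objective response "from 20% (under the null hypothesis) to 50% (under the alternative hypothesis) in the fully matched arm". The design statement there is: "With 5% one-sided type I error, we need to treat 20 patients to demonstrate the usefulness of the tri-therapy approach to achieve and 86% power". The test it names is an exact binomial one, and it asks for 200 patients because 10% are expected to be fully matched.

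Section 1.4 repeats the 7.2.1 version under one of two scenarios for extending the study: "we need to treat 20 patients to demonstrate the usefulness of the tri-therapy approach to achieve and 86% power", again with one-sided 5% and the exact binomial test, but without restating the 20% null.

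None of the three sections prints the number of responders that counts as success, and none says which statement takes precedence.

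**The concern.** The endpoint, arm, null rate, number of fully matched patients and total size agree between 3.1 and 7.2.1. The type I error, the power and the name of the test do not. A primary test should have one decision rule. Here a result near the boundary can be called a success or a failure depending on the section cited. Matching by the SIMS algorithm is analysed retrospectively, so if the rule is not settled beforehand, the choice between two documented cut-offs could be made with the result in view.

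The test name is a second fault. Fisher's exact test compares two observed groups, and its cut-off depends on the comparison group. Section 3.1 compares one group with an assumed fixed rate.

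**Working it through.** **Inputs.** n = 20 fully matched patients (3.1, 7.2.1, 1.4); null rate 0.20 (3.1, 7.2.1); alternative 0.50 (7.2.1); type I error limit 10% (3.1) or one-sided 5% (7.2.1, 1.4).

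**Formula.** X ~ Bin(20, p). The pass mark is the smallest r with P(X ≥ r | 0.20) no greater than the limit. Power is P(X ≥ r | 0.50).

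**Reproducing the plan's figures.**

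| Pass mark r | P(X ≥ r) at 0.20 | P(X ≥ r) at 0.50 |
|---|---|---|
| 6 | 0.1958 | 0.9793 |
| 7 | 0.0867 | 0.9423 |
| 8 | 0.0321 | 0.8684 |
| 9 | 0.0100 | 0.7483 |

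- Limit 10%: r = 6 is too liberal (19.6%), so r = 7. Actual type I error 8.7%, power 94.2%. This is the 94% in 3.1.
- Limit 5%: r = 7 is too liberal (8.7%), so r = 8. Actual type I error 3.2%, power 86.8%. This is the 86% in 7.2.1 and 1.4, apparently truncated.

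Both stated powers are therefore one-sample exact binomial figures.

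**Does a true Fisher test explain the 94%?** A two-sample one-sided Fisher test at 10%, 50% against 20%, with 20 patients against a comparison group of 20 to 180, gives power from 0.68 to 0.89. None of the sizes tried reaches 94%.

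**Where the two rules disagree at n = 20.** Only at X = 7:
- P(X = 7 | 0.20) = 0.0867 − 0.0321 ≈ 0.0545, or 5.5%.
- P(X = 7 | 0.50) = 0.9423 − 0.8684 = 0.0739, or 7.4%.

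**First 100 patients.** With the expected 10 fully matched, P(X ≥ 4 | 0.20) = 12.1% and P(X ≥ 5 | 0.20) = 3.3%. Both limits give 5/10, with power 62.3% at 0.50, so there is no conflict at exactly 10.

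**If the number fully matched varies.** Assume M ~ Bin(N, 0.10), which the plan does not state. For each M = m, let a(m) and b(m) be the 10% and 5% pass marks. The probability of opposite verdicts is the sum over m of P(M = m) × P(a(m) ≤ X < b(m)), with X ~ Bin(m, p):

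| N treated | True rate 20% | True rate 50% |
|---|---|---|
| 100 | 3.8% | 15.9% |
| 200 | 3.4% | 6.7% |

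The two marks coincide at m = 7, 10, 14, 17 and 21, for example, and differ by one responder at 8, 9, 11–13, 15, 16 and 18–20.

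**The case against.** The strongest reply is that little turns on this now. The 20-patient test needs about 200 treated patients. Section 3.1 calls the first 100 exploratory, the extension needs an amendment, and section 7.6 says all findings must be validated in later studies. At the planned 10 fully matched patients the rules agree. Sections 7.2.1 and 1.4 agree with each other, so a reader could treat 3.1 as the outlier. All of this stands, and it limits the weight of the point. It does not remove it, because 3.1 is the section that defines success and the text gives no order of precedence.

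A reader might also infer more than the documents support:

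- **That one of the powers is wrong.** Both reproduce.
- **That the protocol prints 7/20 and 8/20 as pass marks.** It does not. They are implied, and 7/20 follows only once the Fisher label is read as a one-sample binomial test.
- **That the verdict is usually at risk because the two marks usually differ.** Under the binomial assumption the marks differ with probability 69% (N = 100) or 74% (N = 200). Opposite verdicts also need the response count to fall in the one-patient gap, which gives the smaller figures tabulated in the working.
- **That 3.1 requires an observed 50%, i.e. at least 10/20.** That rule has power 58.8%, which does not fit the 94% in the next sentence, and 7.2.1 makes 50% the alternative. The wording is loose, but this is the weaker reading.
- **That superiority over the partially matched arms is a second formal test with a known loss of power.** No test is named. The same section asks for significance elsewhere ("If fully matched patients show significantly better clinical outcomes than the partially matched ones"), so the plain word may mean only numerically higher. Any joint power would rest on a guessed meaning. What stands is that neither stated power covers this condition.
- **That the Bayesian rule in 7.2.1 is a further primary criterion.** The sentence "the treatment will be considered potentially efficacious if we see 4 responses in 10 patients, 7 responses in 20 patients" belongs to a separate subgroup signal rule and is worded as potential efficacy.

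**Conclusion.** The inconsistency is real and should be fixed; its numerical reach is narrow. One primary test carries two type I error rates, two powers and two test names, with implied pass marks of at least 7/20 and at least 8/20. At 20 fully matched patients only a result of exactly 7 is affected. The results rest on reading both sections as a one-sample exact binomial test of 20% against 50%, which reproduces both stated powers. The opposite-verdict probabilities for a varying subgroup size rest further on each patient being fully matched independently with probability 10%.

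**What to change.** State one type I error, one test and one cut-off in responders, identically in 3.1, 7.2.1 and 1.4, before the fully matched results are known.

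- **Default:** replace the design sentence in 3.1 with the 7.2.1 rule: one-sample exact binomial test against 20%, one-sided 5%, pass mark at least 8/20, actual type I error 3.2%, power about 87% at 50%. Print the same pass mark in 7.2.1 and 1.4, and add the 20% null to 1.4.
- **If the sponsor prefers 10%:** state at least 7/20, actual type I error 8.7% and power 94% in all three places.
- **Either way:** drop the Fisher label, word the 50% in 3.1 as the design alternative, and note that the stated power does not cover the added condition of superiority over the partially matched arms.

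The cost is text edits in three sections, with no new data or patients. Under the default, the more favourable stated power of 94% is lost.

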## 1.2. STUDY OVERVIEW

### **1.2.1. The first goal of the SPRING protocol is to test the safety and the activity of the selected tri-therapy in patients with metastatic NSCLC patients in first therapeutic line for the phase 2 portion of the trial (for the phase 1 patients with a maximum of 2 prior lines will be accepted).**

The trial will start with a Phase 1 safety study to establish the dose of each of the three agents. This part of the study will require about 30 patients treated (~40 patients enrolled). The Phase 1 will be followed by a first extension Phase 2 to test efficacy on up to 100 patients who will all receive the tri-therapy (100 patients treated/ ~120 patients enrolled (~20 patients screen failures)). All patients will have the necessary biopsies performed to ensure that adequate biopsy material is available before starting treatment. For ethical reasons, patients whose biopsies fail to produce interpretable data will still be treated with the tri-therapy. Pending clinical activity, the study may be extended by an additional 100 patients treated (total = 200 patients on the phase 2 portion) in order to firm up the initial efficacy assessment and identify the potential subgroups of patients with clinically meaningful efficacy.

Patients with specific documented oncogenic aberrations (EGFR mutations, ALK translocations, ROS1 if available and MET exon 14 skipping mutation if available) will be excluded from the trial. The study cohort will aim to include patients who are not generally treated with specific targeted therapeutics. Patients will be included in the study regardless of their PD1 or PD-L1 expression status. In the case of patients already treated on SPRING protocol who are later determined to have EGFR mutation or ALK translocation or ROS1 or MET exon 14 skipping mutations after SIMS analyses, amenable to treatment with an approved therapy, they will be given the option to continue investigational treatment in the SPRING trial after obtaining appropriate re-consent or discontinue treatment.

Early futility stopping rules will be applied in the phase 2 study should the tri-therapy have less than the expected efficacy to guard against patients being enrolled in ineffective treatment.

We estimate that overall 85% of the patients treated in the trial will have a profile that is matched to at least one out of the three drugs: 10% matched with three drugs, 36% matched with two drugs and 39% matched with one drug.

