The proposed study is a proof of concept protocol to evaluate the outcome of patients who receive triple therapy and to evaluate through a retrospective analysis, the clinical utility of the SIMS algorithm and integrated genomic/transcriptomic analysis. For the selected triple combination therapy, we will incorporate a seamless Phase 1/2 design with a limited Phase 1 run-in to determine the recommended Phase 2 dose for the regimen. Patients enrolled in the phase 1 study who receive the RP2D will also be included in the phase 2 efficacy assessment. In the first part of the phase 2 study, up to 100 patients will receive the triple combination therapy and all will have dual biopsies in order to obtain the full set of genomic and transcriptomics data resulting from the investigation of matched tumor and normal biopsies. The population for analysis of response (evaluable patients) will be those that received at least one cycle of treatment. The SIMS algorithm will not be used prospectively to assign patients to treatment. However, it is expected that the SIMS score for each patient will be available within 3 months after the treatment start date. SIMS algorithm will be used retrospectively for defining patient subgroups and correlation correlating with treatment outcome. Patients will be stratified into the fully matched group (Arm A) with all three interventional points activated, or partially matched group, with one or two interventional points activated (Arms B1-B3, C1-C3) or the non-matched group (Arm C4) (see study schema). In addition, after completion of the clinical trial, a correlation study will be performed between patients' clinical outcomes and the predicted match determined by SIMS and all potential prognostic and predictive variables. The primary endpoint for this study is defined as the 6-month objective response rate (by RECIST 1.1 criteria as percent of patients achieve complete response, or partial response). We choose the 6-month response rate for an early efficacy read of the triple therapy. Other efficacy endpoints may include best overall response rate, progression-free survival (PFS), overall survival (OS). The expected result is a better clinical outcome in the fully matched patients arm (arm A) as compared to the partially matched or the non-matched patients' arms.

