Also we will compare the estimated numbers of patients in each of the arms as predicted by SIMS versus the observed distribution in the patients treated. Based on previous data published (1), the estimated match in PD-L1 positive (50 patients) is:

- Arm A: Fully matched group, with all three activated targets, will be seen in 10 patients.
- Arms B1 or B2: Partially matched group, with two activated targets (anti PD-L1 + CDK4/6 or anti PD-L1 + anti VEGFR), will be seen in 13 patients and 12 patients respectively.
- Arm B3: Remaining 15 patients will only be matched to anti PD-L1.

For the PD-L1 negative patients (50 Patients), they are further grouped into the following 4 subgroups:

- Arm C1: Partially matched group with two activated targets (CDK4/6 and VEGFR), will be seen in 11 patients.

- Arm C2 or C3: Partially matched group with one activated targets (VEGFR or CDK4/6), will be seen in 8 and 16 patients, respectively.
- Arm C4: Non-matched group, with none of the three activated target matched, will be seen in 15 of patients.

It is expected that half of the patients will be PD-L1 positive and half of the patients will be PD-L1 negative. The hypothesized 6-month response rate in Arm A (fully matched) is 50%; in Arms B1, B2, and C1 (partially matched with two targets) is 40%; in Arm B3 (matched with PD-L1 only) is 30%; in Arms C2 and C3 (partially matched with VEGFR or CDK4/6) is 20%; and in Arm C4 (non-matched group) is 10%. The expected 6-month response rate is 30% in the entire group assuming the triple therapy works.

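### Section 3.1 compares the fully versus partially matched split in the whole cohort with 20/80, but section 7 predicts 10:75 (11.8/88.2 of matched patients) for that cohort, and the 20% tolerance has no definition

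*Combined protocol and SAP*

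**What the plan says.** Section 3.1 (Criteria of success) gives two conditions for SIMS clinical utility. The first is "If the proportion of patients fully matched to the combination versus partially matched estimated using SIMS (20/80) is similar to the observed proportion", and the sentence continues "in the SPRING cohort (maximum coefficient variability allowed 20" (per cent). No PD-L1 restriction is stated, and patients enrol regardless of PD-L1 status. The second condition concerns outcomes: fully matched patients must do better than partially matched ones, and matched better than non-matched.

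Section 7 defines the groups. Fully matched is Arm A; a patient falls into the "or partially matched group, with one or two interventional points activated (Arms B1-B3, C1-C3") or the non-matched Arm C4. It then gives predicted counts per 100 patients: "the estimated match in PD-L1 positive (50 patients) is" followed by Arms A and B1 to B3, then Arms C1 to C4 for the 50 PD-L1-negative patients. For the fully matched group: "Arm A: Fully matched group, with all three activated targets, will be seen in 10 patients". Section 1.2.1 gives the same prediction as percentages: "10% matched with three drugs, 36% matched with two drugs and 39% matched with one drug".

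Section 7 also plans its own comparison: "Also we will compare the estimated numbers of patients in each of the arms as predicted by SIMS versus the observed distribution". Section 7.2.1 repeats the 20% tolerance for observed against estimated matches. Neither 3.1 nor 7.2.1 gives a formula for it, names the quantity it applies to, or says whether it is relative or absolute.

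**The concern.** A success condition should compare an observed quantity with the plan's own prediction for the same population. Here the population named is the whole cohort, but the figure is not the whole-cohort prediction in section 7. The two sections can therefore give opposite verdicts on the same data: section 7 would find the arm counts exactly as predicted, while 3.1 could find the split too far from 20/80.

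The undefined 20% makes this worse, because the choice of reading decides the result. Unless it is fixed beforehand, it could be chosen once the SIMS results are known. At stake is whether SIMS is declared clinically useful. Validating SIMS is the trial's second goal, and correlating outcome with SIMS matching is listed among the primary objectives.

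**Working it through.** **Inputs.** Arm counts per 100 patients (section 7): A 10, B1 13, B2 12, B3 15 (50 PD-L1 positive); C1 11, C2 8, C3 16, C4 15 (50 PD-L1 negative). Partially matched is B1-B3 plus C1-C3 (section 7).

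**Reproducing the plan's totals.**
- Two targets: 13 + 12 + 11 = 36. One target: 15 + 8 + 16 = 39. These agree with the 36% and 39% in section 1.2.1.
- Partially matched: 36 + 39 = 75. All matched: 10 + 75 = 85. With 15 non-matched, the total is 100.

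**Looking for 20/80.**

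| Split | Counts | Share |
|---|---|---|
| Whole cohort, fully vs partially matched | 10:75 | 11.8/88.2 |
| Whole cohort, fully matched vs all others | 10:90 | 10/90 |
| PD-L1 positive, A vs B1-B3 | 10:40 | 20/80 |
| Fully matched vs one-target only | 10:39 | 20.4/79.6 |
| Fully matched vs two-target only | 10:36 | 21.7/78.3 |
| PD-L1 positive, A vs B1-B2 | 10:25 | 28.6/71.4 |

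Only the PD-L1-positive arms give 20/80 exactly. The 10:39 and 10:36 splits come close, but each leaves out part of the partially matched group that section 7 defines.

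**A cohort exactly on the section 7 counts, judged against 20/80.**
- Relative, fully matched share: (20 - 11.76)/20 = 41%. Fails.
- Coefficient of variation of the two values 20 and 11.76 (mean 15.88, difference 8.24): sample SD 8.24/√2 = 5.82, and 5.82/15.88 = 37%; population SD 8.24/2 = 4.12, and 4.12/15.88 = 26%. Both fail.
- Percentage points: 20 - 11.76 = 8.2. Passes.
- Relative, partially matched share: (88.24 - 80)/80 = 10%. Passes.

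**How often the condition is met if section 7 is exactly right.** Let N be the number of patients with a SIMS result. The number matched is M ~ Binomial(N, 0.85) and the number fully matched is X | M ~ Binomial(M, 10/85). For the PD-L1-positive version, M ~ Binomial(N, 0.5) and X | M ~ Binomial(M, 0.20). The pass probability is the sum over M of P(M) × P(X/M within the limits | M).

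| Benchmark and reading of the 20% | N = 100 | N = 200 |
|---|---|---|
| 20/80, relative (16% to 24%) | 12% | 5% |
| 20/80, CV with sample SD | 17% | 10% |
| 20/80, CV with population SD | 32% | 26% |
| 20/80, percentage points (0% to 40%) | about 100% | about 100% |
| 20/80, relative on the partially matched share (64% to 96%) | 99% | above 99% |
| 11.8/88.2, relative (9.4% to 14.1%) | 51% | 66% |
| 20/80 in PD-L1-positive patients only, relative | 53% | 68% |

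The denominators are allowed to vary for a reason. With exactly 85 matched patients, the limits around 11.8% fall on whole counts (8/85 and 12/85) and the rate rises to 60%. The same happens with exactly 50 PD-L1-positive patients (8/50 and 12/50), where it is 62%. Those values flatter the corrected benchmark.

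**Missing SIMS results.** Section 1.2.1 allows for them: "patients whose biopsies fail to produce interpretable data will still be treated with the tri-therapy". The documents give no failure rate. If 80% of patients had a result (an assumption), N becomes 80 or 160. The relative pass rates are then 14% / 7% against 20/80 and 45% / 61% against 11.8%.

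**The case against.** The strongest objection is that the origin of 20/80 is inferred. The protocol never says it is the PD-L1-positive prediction. The study schema that section 7 points to is a figure not shown in the available text, and it might carry the restriction. This stands: the match with 10:40 is arithmetic, not a statement by the sponsor, and what is said here is limited to the visible text.

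Second, 3.1 asks only that the splits be similar and names no formal test, and the result depends on the reading. This also stands. A reader might infer that an accurate SIMS prediction is bound to fail 3.1. The documents do not support that, because two of the possible readings of the 20% would pass it almost always.

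Third, the consequences are limited. Section 7 uses the arm counts rather than 20/80, section 3.1 calls the first 100 patients exploratory, and section 7.6 says all findings need validation. All true. But the condition in 3.1 is still a stated criterion, and it still names a figure that does not belong to the population it names.

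A reader might also infer that the sample size rests on the wrong matching rate. It does not: section 7.2.1 sizes the study on 10% fully matched, in line with the section 7 counts.

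**Conclusion.** The condition is wrong as written. Section 3.1 pairs a 20/80 split with the whole cohort, for which section 7 predicts 11.8/88.2. Either the figure is wrong or a PD-L1 restriction is missing, and the visible text does not settle which.

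If section 7 is right, a relative or CV reading of the 20% would usually reject an accurate prediction: the chance of meeting 20/80 within 20% relative is about 12% with 100 patients and 5% with 200. A percentage-point reading would almost never reject it. The rates assume binomial sampling, predicted shares that are exactly true, and a SIMS result for every patient.

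The harm is confined to the SIMS utility condition. No treatment, stopping or sample-size rule depends on it, and the outcome-based second condition is untouched. Correcting the benchmark does not by itself make the condition reliable: on the relative reading, an exactly correct prediction would still pass only about half to two thirds of the time.

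**What to change.** In section 3.1, make the figure and the population agree, and state that the figure is derived from the section 7 arm counts. Either:

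- (a) 10/75, that is 12/88 of matched patients, in the SPRING cohort; or
- (b) 20/80 among patients with PD-L1 activated by SIMS (score above 5). Naming the SIMS score matters because section 1.1 also records PD-L1 results from IHC tests.

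Keep the sponsor's 20% limit. State in both 3.1 and 7.2.1 which quantity it applies to and whether it is relative, absolute or a coefficient of variation, with the formula. Fix this before SIMS results are seen.

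Optionally, report the observed fully matched share with an exact 95% confidence interval, and the number of treated patients without an interpretable SIMS result. This should be description only. Making inclusion of the prediction in the interval the criterion would remove the sponsor's pass/fail limit, and it would become easier to satisfy as SIMS results are lost.

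The cost is a wording change in two sections, with no new data. The sponsor has to choose one reading of the 20% and accept its pass rate.

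### Sections 3.1 and 7.2.1 set different outcome conditions for SIMS success: significance in two comparisons in one, a numerically better result in one comparison in the other

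*Combined protocol and SAP*

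**What the plan says.** The protocol gives two rules for judging SIMS a success. Each joins a condition on how often patients match to a condition on outcome.

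- **Section 3.1, Criteria of success.** The fully to partially matched split should be close to 20/80 ("maximum coefficient variability allowed 20" percent). The outcome condition is "If fully matched patients show significantly better clinical outcomes than the partially matched ones", and in addition that "the fully or partially matched ones show significantly better clinical outcomes than the non-matched ones".
- **Section 7.2.1, closing paragraph.** "SIMS model will be considered clinically meaningful if the observed matches are similar to estimated matches", again with a 20% tolerance, "and if fully matched group shows better outcome than partially matched groups".

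Neither place names the outcome, the test, the alpha or the sidedness for these comparisons. Other type I error levels appear nearby for a different question, the single-arm test in fully matched patients: 10% in section 3.1 and one-sided 5% in section 7.2.1. Section 7.6 states that multiplicity will not be adjusted for and that findings need validation in later studies.

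**The concern.** The 7.2.1 outcome clause drops both the word that makes 3.1 a statistical criterion and the whole comparison with non-matched patients. Read as written, any numerical advantage of the fully matched group satisfies it. Because no text ranks the two rules, the analyst can reach opposite conclusions on the outcome condition from one dataset, depending on the section followed.

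Evaluating SIMS is one of the trial's two stated goals, and correlating outcome with SIMS matching is listed among the primary objectives. If the rule is chosen after SIMS scores have been linked to outcomes, the choice is open to influence by the data.

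**Working it through.** **Inputs.** Arm sizes per 100 treated and hypothesised 6-month response rates are from the opening of section 7: Arm A 10 patients (50%); B1 13, B2 12 and C1 11 (40%); B3 15 (30%); C2 8 and C3 16 (20%); C4 15 (10%). So 10 are fully, 75 partially and 15 non-matched. At 200 treated the sizes double to 20, 150 and 30.

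**The plan's own figures.** The primary test concerns a change "from 20% (under the null hypothesis) to 50% (under the alternative hypothesis) in the fully matched arm". With X binomial and n = 20:

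- Success at 8 or more responses: P(X ≥ 8 | 0.2) = 0.032 and P(X ≥ 8 | 0.5) = 0.868. This reproduces the stated 5% and 86%.
- Success at 7 or more: 0.087 and 0.942. This reproduces the 10% and 94% of section 3.1.
- Whole group: (10×0.5 + 36×0.4 + 15×0.3 + 24×0.2 + 15×0.1)/100 = 30.2%, stated as 30%.
- Partially matched, pooled: (36×0.4 + 15×0.3 + 24×0.2)/75 = 23.7/75 = 31.6%.

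**One dataset, two verdicts.** Take results close to expectation at 200 treated: 10/20 fully, 47/150 partially and 3/30 non-matched.

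- 7.2.1 outcome clause: 50% exceeds 31.3%, so it is met.
- 3.1 outcome clause: fully against partially gives Fisher p = 0.082 one-sided (0.129 two-sided). Matched against non-matched (57/170 against 3/30) gives p = 0.006 one-sided. The clause fails at one-sided 5% and passes at one-sided 10%.

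**How often the outcome clauses are met.** Exact enumeration of the binomial responses. Assumptions: the outcome is 6-month response, the six partially matched arms are pooled, and each 3.1 comparison uses a one-sided Fisher test. The 7.2.1 clause is met when the observed fully matched rate exceeds the pooled partially matched rate; the 3.1 clause when both tests are significant. No value means 30% response in every group.

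| Treated | Truth | 7.2.1 clause | 3.1 clause, 5% | 3.1 clause, 10% |
|---|---|---|---|---|
| 100 | no value | 48.2% | 0.06% | 0.34% |
| 200 | no value | 48.2% | 0.10% | 0.43% |
| 100 | plan's rates | 85.9% | 10.4% | 23.2% |
| 200 | plan's rates | 93.9% | 34.7% | 50.1% |

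With two-sided 5% tests, the 3.1 clause at the plan's rates is met 7.1% (100) and 28.1% (200) of the time.

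**Chance of disagreement at the plan's rates.** Under pooling, meeting 3.1 implies meeting 7.2.1, so this is the difference between the columns. At 5% it is about 75% with 100 treated and 93.9 − 34.7 = 59% with 200. At 10% it is 63% and 44%. The limiting test is fully against partially matched: at 200 treated and 5% it is significant 39.6% of the time, against 87.1% for matched against non-matched.

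**The frequency condition.** The two sections share only the 20% tolerance. Section 3.1 uses 20/80. The section 7 estimates, which 7.2.1 relies on, give 10 fully to 75 partially matched, or 10/85 = 11.8% to 88.2%. The 20/80 split fits only the PD-L1-positive half (10 of 50 fully, 40 of 50 partially matched). The tolerance is undefined. As an illustration, read it as within ±20% of the target, with the section 7 proportions true:

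- 7.2.1, applied to the fully matched count: 8–12 of 100 has probability 60%, and 16–24 of 200 has 71%.
- 3.1, applied to a fully matched share of 16–24% of matched patients: 14–20 of 85 has probability 12%, and 28–40 of 170 has about 4%.

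**The case against.** The best defence is that little hangs on this. SIMS is applied retrospectively and does not guide treatment (section 1.1). The first 100 patients are described as exploratory (section 3.1), extension to 200 needs an amendment, and findings need later validation (section 7.6). The primary endpoint has its own criterion. All of this stands, and it makes this a wording defect to reconcile rather than a threat to the trial. None of it says which SIMS rule applies.

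It can also be said that clinical utility and clinically meaningful are different labels, or that 7.2.1 is shorthand for 3.1. The plan does not define two tiers of success, and the statistical section is where an analyst looks for the operative rule.

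A reader might go further than the documents allow in three ways:

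- **That 7.2.1 would declare a worthless SIMS successful about half the time.** The 48% covers the outcome clause alone. On the illustrative frequency reading, joint success is roughly 0.48 × 0.60 = 29% at 100 and 0.48 × 0.71 = 34% at 200. The wording of 7.2.1 also speaks of partially matched groups in the plural. If the fully matched group had to beat each of the six arms, a worthless SIMS would meet the outcome clause only about 15% of the time.
- **That a SIMS working as hypothesised usually fails 3.1.** With 200 treated this depends on choosing 5%. The only type I error stated in section 3.1 is 10%, given for the primary test, and at that level the outcome clause is met half the time. With 100 treated it fails more often than not at either level.
- **That both sections apply the same frequency condition.** They do not, as shown above.

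**Conclusion.** The contradiction holds in the current text. Section 3.1 requires significance for fully against partially matched and for matched against non-matched; section 7.2.1 requires only a better result for the first. The conflict runs one way: with partially matched arms pooled, data meeting the 3.1 outcome clause always meet the 7.2.1 clause, but not the reverse.

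For that clause alone, a SIMS with no value passes 7.2.1 about 48% of the time and 3.1 at most 0.1% at 5% alpha (about 0.4% at 10%). At the plan's rates the two clauses disagree in 44% to 59% of trials with 200 treated and 63% to 75% with 100, over one-sided alphas of 10% and 5%. These figures rest on 6-month response as the outcome, pooled arms and one-sided Fisher tests, none of which the plan specifies for these comparisons. They are not probabilities of full SIMS success, which is lower under either section because the frequency condition must also hold. The missing alpha can itself decide the result, as p = 0.082 shows.

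This should be fixed, but it does not affect treatment or the primary test.

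**What to change.** State one SIMS success rule, word for word the same in 3.1 and 7.2.1, before SIMS scores are linked to outcomes.

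- Replace the 7.2.1 outcome clause with the two significance comparisons of 3.1: fully against partially matched, and fully or partially matched against non-matched. Both must pass, so no multiplicity adjustment between them is needed.
- Name the endpoint (for example 6-month response), how the partially matched arms are pooled, a one-sided exact test, and a single alpha. The plan uses both 5% and 10% elsewhere, so the choice must be explicit.
- Reconcile the 20/80 target with the section 7 estimates of 10 fully and 75 partially matched per 100, and define the 20% tolerance.
- State the power at the chosen alpha, labelled as applying to the outcome clause only: about 35% at 200 treated and 10% at 100 for 5%; about 50% and 23% for 10%.
- Report a numerically better but non-significant difference as an estimate with a confidence interval, not as SIMS success.

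The cost is wording in two sections and a less favourable stated chance of declaring SIMS useful. No extra patients or assessments are needed.
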